3.1 Study population

All women attending screening mammography at Capio S:t Göran hospital will be considered for inclusion. The ethical review authority has waived the need to obtain individual written informed consent.

- Inclusion criterion: age 40-74 years, a standard four-view mammography examination was acquired (right MLO, right CC, left MLO, left CC)

- Exclusion criteria: having a breast implant (excluded by presence of either CCID or MLOID view position; ID = implant displaced) or having undergone mastectomy (excluded by not having a complete four-view mammography).

3.2 Study period

The study will start as soon as all technical component are in place and integrated, currently predicted to be February 2021. The duration of inclusion of study persons will depend on when 55,000 women has been included in the study, which we assess to be around 1,5 years.

UPDATE: The first study person was included on April 1, 2021, and the study is estimated to close inclusions in May or June, 2022. Then, for the final analyses of interval cancer cases there is a need for 23-month follow-up after the last included patient. An overview is shown in Figure 3 below.

4 Objectives and Endpoints

The purpose of the study is to examine the integration of an independent AI computer-based reader into a population-based screening program. First, in the initial read and decision to flag suspicious examinations, we will determine whether AI and one human radiologist is non-inferior to two human radiologists - in terms of detecting breast cancer. Second, we will estimate the operating characteristics of various combinations of AI and radiologists, in the initial read and in the arbitration step, as described in Figure 2.

4.1 Primary endpoint

Diagnosed pathology-verified breast cancer; to be followed up at three time-points: (i) screen-detected - diagnosed after being recalled at the screening examination, (ii) adding non-screen-detected cancer diagnosed within 12 months after the screening examination and (iii) adding non-screen-detected cancer diagnosed within 23 months after the screening examination, not including the following screening examination (such that all cancers diagnosed over a full screening cycle are captured).

4.2 Secondary endpoints

4.2.1 Reader flagging of women evaluated as cancer free [YES|NO], i.e., each reader (radiologist or AI) makes an assessment that there is an abnormal finding warranting the examination to continue to the consensus discussion. Radiologist id codes will be recorded.

4.2.2 Consensus recall of women evaluated as cancer free [YES|NO], i.e., a decision by the consensus discussion to recall the woman for further work-up. Radiologist id codes will be recorded.

4.2.3 Tissue sampling of women evaluated as cancer free [YES|NO], i.e., decision by the radiologist to perform tissue sampling after additional diagnostic imaging of a recalled woman.

4.2.4 Process failures in generating the AI score or in transferring the AI score to the appropriate datapoint in the radiological RIS/PACS system.

4.3 Additional data collected in the study

4.3.1 Patient characteristics

4.3.1.1 All women

- age at diagnosis: median and categorized into (i) 55 years or less and (ii) more than 55 years to approximate pre- and postmenopausal groups.
- mammographic density by automated classification mimicking BI-RADS categories A, B, C, D

4.3.1.2 Diagnosed women

- reduction surgery, lipo-filling, biopsy markers and surgical clips, pacemakers or other non-breast implants.

4.3.2 Cancer characteristics

- invasiveness by categories: in-situ only, invasive
- histology by categories: ductal, lobular, other
- tumor grade by categories: 1, 2, 3
- lymph node metastasis by categories: 0 nodes, 1-3 nodes, 4+ nodes
- tumor size, median size of invasive component and in situ component
- invasive tumor size by binary categories: (i) 0-19 mm, (ii) 20 mm+;
and by five categories: 0-9 mm, 10-19 mm, 20-29 mm, 30-49 mm, 50 mm+
- receptor status ER, PR, HER2 by categories: positive, negative
- proxy molecular subtype defined by:
 - Luminal A: ER+/PR+/HER2-; ER+/PR-/HER2-; ER-/PR+/HER2
 - Luminal B : ER+/PR+/HER2+; ER+/PR-/HER2+; ER-/PR+/HER2+
 - Non-luminal HER2-overexpressing: ER-/PR-/HER2+
 - Triple negative: ER-/PR-/HER2-

4.4 Exploratory objectives and endpoints

4.3.1 The first exploratory objective is to examine how different choices of AI prediction score cut-off point affects the operating characteristics. Exploratory end-points: the image-level AI prediction scores for each of the four views in the screening examination; the exam-level AI prediction score defined by the maximum image-level score.

4.3.2 The second exploratory objective is to assess how the cancer and patient characteristics listed above affect the diagnostic performance of the various combinations of radiologists and AI (Figure 2), (i.e. to test whether there are interactions between patient of cancer characteristics and diagnostic performance).

4.3.3 The third explorative objective is to determine how cancer detection and false positive flagging would be affected by combining AI with radiologists with varying sensitivity and specificity (the sensitivity and specificity of each individual radiologist in flagging in the initial read, and of each combination of radiologists in the consensus discussion).

4.3.4 The fourth exploratory objective is to explore how the AI flagging affects the consensus discussion in terms of the number of cases, the time required by radiologists and to what extent the radiologists in the consensus discussion take the AI information into account, how that changes over time and potential determinants (in addition to the end-points above we will issue repeated questionnaires based on technology acceptance models to the staff involved in the study and measure the time duration of a sample of consensus discussions).

4.3.5 The fifth explorative objective is to assess what the operating characteristics of AI and radiologist was for the following excluded groups had not been excluded: prior breast cancer, breast implants, partial mastectomy, reduction surgery, lipo-filling, biopsy markers and surgical clips, pacemakers or other non-breast implants.

4.3.6 In addition, we will perform exploratory reader studies to understand potential image-related causes of AI false negative and false positive initial read decisions.

5 Statistical methods

All analysis will take place after the relevant end-point(s) has been measured for all study persons. To be explicit, the **fourth explorative objective** above does not require any end-points in terms of cancer detection, but concerns the radiologists' behavior in the consensus discussion and specifically their adherence to the AI decisions. Since it will provide no information on whether the AI system performs well or not, the analysis can be performed before the inclusion has ended.

Analysis based on screen-detected cancer as ground truth will be performed at the earliest 1 month after the mammogram of the last included study person has been acquired and the first version of the database has been released (Figure 3). Analyses including clinical cases will be performed according to the definition of the primary end-point following the release of the database in its second and third version respectively. All statistics, including tables, figures and listings, will be performed using Stata version ≥ 16 or R version ≥ 4.0 .

The data structure in the study will have the following outline (where the endpoint=negative 2x2 table will be constructed for each stage of radiological assessments: 1. Reader flagging; 2. Consensus discussion; 3. Tissue sampling (biopsy)):

	Endpoint = positive (yes)		Endpoint = negative (no)	
	SOC positive	SOC negative	SOC positive	SOC negative
Positive using novel reader combination including AI positive	a	b	e	f
Negative using novel reader combination including AI negative	c	[d]	g	[h]

Here, SOC denotes standard of care (defined as two human radiologists). The SOC can then be compared with respect to number of endpoint positive (cancers detected) and endpoint negative (no cancer detected) with novel reader combinations including AI (Figure 2).

It should be noted that since only patients who screen positive on either SOC or SOC together with AI are referred for further work-up, the number of patients reported between brackets are unknown. This is a feature of the screen-positive design and means that absolute sensitivity and specificity cannot be estimated.

Analyses will compare the true positive fraction between different combinations of readers (radiologists or AI). Comparisons will be made on a relative scale. The relative true positive fraction (rTPF) is defined as TPF_r/TPF_{SOC} , where TPF_r is a specific reader combination r (Figure 2) being compared with the TPF of using two radiologists (SOC). The analysis will largely follow the methods described by Pepe and Alonzo (10).

The rTPF is estimated as $(a+b)/(a+c)$ (or $(a+c)/(a+b)$, as appropriate) and an approximate $100(1-\alpha)\%$ two-sided confidence interval for rTPF is calculated as

$$\exp\left(\log(\widehat{rTPF}) \pm z_{\alpha/2} \sqrt{\frac{b+c}{(a+b)(a+c)}}\right).$$

Analogous formulas are used for comparisons within the experimental arm and for the relative False Positive Fraction.

Non-inferiority and superiority tests

For comparisons of the rTPF, the null and the alternative hypothesis for non-inferiority and superiority tests are

$$H_0: rTPR \leq \exp(-\delta)$$

$$H_a: rTPR > \exp(-\delta)$$

and

$$H_0: rTPR \leq \exp(\theta)$$

$$H_a: rTPR > \exp(\theta)$$

respectively, with non-inferiority and superiority margins equal to $\delta > 0$ and $\theta \geq 0$.

One-sided p-values will be calculated based on the test considered (non-inferiority or superiority).

Switching from non-inferiority to superiority: if the two-sided $(2(1 - \alpha) \times 100)\%$ confidence interval for rTPF not only lies entirely above the non-inferiority margin, but also above the superiority margin, superiority will be claimed at the same alpha-level set for the non-inferiority test. In this case, we will also calculate the p-value associated with a test for superiority.

We will assess the non-inferiority of novel reader combinations involving AI versus SOC for detecting cancers ($\exp(-\delta) = 0.85$). The one-sided α level is set to 0.025. Two-sided 95% confidence intervals will be reported.

For the secondary endpoints, the relative false positive fraction (rFPF, defined as FPF_r/FPF_{SOC} for reader combination r) will be assessed at each stage of radiological assessments: 1. Reader flagging; 2. Consensus discussion; 3. Tissue sampling (biopsy). The rFPF is estimated as $(e+f)/(f+g)$ for each stage of radiological assessments and confidence intervals are computed analogously to the rTPR.

Heterogeneity of treatment effect

Subgroup analyses will be performed for patient and cancer characteristics listed in 4.3 Additional data collected in the study. Statistical tests for effect heterogeneity across subpopulations will be performed by jointly testing the interaction (product) terms in generalised linear models or marginal models(10), as appropriate. No correction for multiple comparisons will be made.

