5.6 Exploratory analyses

5.6.1 Determine the initial read operating characteristics of a binary detection at each possible cut-off point for the AI scores based on the ground truth of cancer defined by end-point 4.2.1 and 4.2.2.

5.6.2 Determine the sensitivity of radiologist and AI depending on mammographic density (divided into four categories) and patient age (divided by 10-year intervals).

5.6.3 Determine whether the joint decision by AI and radiologist is more often false positive or false negative depending on the overall sensitivity and specificity of the radiologist with whom the AI decision is combined.

5.6.4 a) Sample the time and number of cases for a sample of consensus discussions during one or more weeks before use of the AI system, and at various time-points after taking the AI system

into use. Compare if there is a difference in the total time of consensus discussion for a standardized number of screening examinations, and if there is a difference in the time per case in the consensus discussions. b) Distribute a query based mainly on the Technology Acceptance Model 3 to all staff, and especially important to the radiologists participating in the consensus discussion. Have radiologists complete a mini-survey at the end of each consensus discussion.

5.6.5. a) Determine the operating characteristics of AI and radiologist for the following excluded groups: prior breast cancer and breast implants. b) To the extent possible, determine the sensitivity of flagging by radiologist and by AI for diagnosed women stratified by each characteristic listed in 4.3.1.2.

5.6.6 Determine differences in visual radiological characteristics between cases (i) not flagged by AI and (ii) not flagged by a radiologist to determine systematic differences between the two groups.

5.6.7 Examine a random selection of healthy women flagged by AI but not by any of the two initial read radiologists, and not recalled, to understand to what extent prior images or clinical information could have contributed to or averted a false positive read.

5.6.8 Examine all cases where at least one reader (AI or any radiologist) made a true positive initial read and at least one reader (AI or any radiologist) made a false negative initial read. Perform a reader study to identify potential image-related findings explaining the false negative assessments.

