5.6.9 Examine the tendency of the consensus discussion to make more false-negative or more false-positive assessments (in terms of end-point 4.2.2 including interval cancers) depending on whether the initial read assessments were concordant, discordant with AI flagging and no radiologist, discordant with one radiologist flagging, other discordant flagging.

5.6.10 Determine the sensitivity difference between the combinations of AI and radiologists stratified by women 40-41 years old (initial screen) and women in subsequent screens.

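### Agreement between AI and consensus cannot by itself show how far consensus takes AI into account, and the adherence measure is left undefined

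*Combined protocol and SAP*

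**What the plan says.** **The question.** SAP 4.4, item 4.3.4, sets out to "explore how the AI flagging affects the consensus discussion in terms of the number of cases, the time required by radiologists", and to learn "to what extent the radiologists in the consensus discussion take the AI information into account, how that changes over time and potential determinants". These are questions about influence.

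**The measure.** SAP section 5 says this objective concerns the radiologists' "behavior in the consensus discussion and specifically their adherence to the AI decisions", and that it "does not require any end-points in terms of cancer detection". Adherence gets no formula, denominator or comparator there or elsewhere.

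**Other sources.** Item 4.3.4 adds timing of a sample of discussions and states that "we will issue repeated questionnaires based on technology acceptance models to the staff involved in the study". The matching analysis, 5.6.4, compares duration and number of cases before and after AI was introduced, uses a technology-acceptance query, and adds: "Have radiologists complete a mini-survey at the end of each consensus discussion". It contains no analysis of recall decisions. Section 5.6.9 looks at the balance of consensus errors "depending on whether the initial read assessments were concordant, discordant with AI flagging and no radiologist", among other patterns.

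**The setting.** Any flag by either radiologist or AI sends an exam to consensus (protocol, Study Type). AI information is open during consensus (protocol, Study Type and Blinding; SAP section 3). The first reader does not see AI. The exam-level AI score is recorded (SAP 4.4, item 4.3.1) and the cut-off is fixed at 0.534 (SAP 5.3). The protocol's Intervention Description allows software updates during the study.

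**The concern.** An exam that AI flags is on average more suspicious than one it does not flag. A consensus group that never looked at the AI output would still recall such exams more often, because it sees the same lesion. Agreement is therefore influence plus shared image evidence, and separating the two needs some information on what consensus would have decided without the flag.

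Nothing planned supplies it. No AI-blinded consensus decision is recorded. The pre-AI sample covers time and case counts, not recall. Questionnaires and mini-surveys are self-report. Section 5.6.9 addresses errors, which is another question. A change in agreement over time is open to the same doubt, since case mix or the AI software version may change while trust does not.

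At stake is the reading of an exploratory result: agreement could be taken for reliance on AI, or real reliance could be missed, and the documents give no basis for telling which.

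**Working it through.** The plan states no figure for adherence or influence, so there is none to reproduce. The check asks what adherence would look like if consensus ignored AI entirely.

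**1. A case that can be followed by hand**

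*From the SAP:* 55,000 exams and prevalence 0.5% (5.7); AI sensitivity 81.9% and first-reader sensitivity 77.4%, the latter used for both radiologists (section 2).

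*Assumed, because the documents give no values:* false-positive flags 4% per radiologist and 6% for AI; readers independent given cancer status; consensus recalls 95% of cancers and 20% of non-cancers whatever AI says.

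There are 55,000 × 0.005 = 275 cancers and 54,725 non-cancers.

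Exams flagged by exactly one radiologist:
- Cancers: 275 × 2 × 0.774 × 0.226 = 96.2. Non-cancers: 54,725 × 2 × 0.04 × 0.96 = 4,202.9.
- AI also flagged: 96.2 × 0.819 = 78.8 cancers and 4,202.9 × 0.06 = 252.2 non-cancers. Recall = (0.95 × 78.8 + 0.20 × 252.2) / 331.0 = 37.9%.
- AI did not flag: 17.4 cancers and 3,950.7 non-cancers. Recall = (0.95 × 17.4 + 0.20 × 3,950.7) / 3,968.1 = 20.3%.
- Gap with zero influence: about 17.5 points.

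All consensus exams:
- AI flagged: 275 × 0.819 = 225.2 cancers and 54,725 × 0.06 = 3,283.5 non-cancers. Recall = 24.8%.
- AI did not flag but a radiologist did: 275 × 0.181 × (1 − 0.226²) = 47.2 cancers and 54,725 × 0.94 × (1 − 0.96²) = 4,033.0 non-cancers. Recall = 20.9%.
- Gap with zero influence: 3.9 points.

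The second gap is smaller because of selection. At consensus an AI-negative exam always carries a radiologist flag, whereas AI-positive exams include AI-only flags, most of which are dismissed.

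**2. Range over the assumptions, zero influence throughout**

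| Model | Radiologist-flagged exams | All consensus exams |
|---|---|---|
| As in step 1; radiologist false positives 2–4%, AI 3–6%, recall 90–95% of cancers and 10–40% of non-cancers | +13 to +43 points (exactly one radiologist) | +2 to +9 |
| Shared latent signal, loadings 0.3–0.8, allowed to differ between radiologists and AI | +7 to +21 points (exactly one radiologist) | −10 to +16 |
| Latent correlation 0.2–0.5; flags 5% per radiologist and 6% AI; 35% recall of radiologist-flagged exams | +12 to +24 points (first-reader flags; 19 at correlation 0.35) | +2 to +7 |

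Raw agreement between recall and the AI flag is no more informative. It is 41–68% in the first two models, and still 55–70% in the second with no shared signal at all.

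**3. Can the stored data do better?**

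The first reader is blind to AI and every first-reader flag reaches consensus, so membership of this set cannot jump at 0.534. Only the AI flag switches there, while suspicion should vary smoothly with the score. In the third model, recall was fitted as a cubic in the AI score plus a step:
- Zero influence: step within about 1 point of 0 (SD 3 to 5), against a raw gap of 12 to 24.
- AI flag turns 20% of dismissals into recalls: step about 11 to 12 points (SD 4 to 5), against a raw gap of 24 to 33.

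A raw gap of about 24 points thus arises both with no influence and strong shared signal, and with real influence and weak shared signal. The pooled step separates the two.

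**4. Limits of the step**

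- *Graded influence.* If consensus responds smoothly to a displayed score, the step largely misses it. Score-driven influence that raised recall of AI-flagged exams by 15 points gave a step of about 5 (SD 4) in one version and near 0 in another.
- *Time.* April 2021 to May or June 2022 is about five quarters. A pooled SD of 3 to 5 points becomes 3 × √5 = 6.7 to 5 × √5 = 11.2 per quarter, and √2 times that, 9.5 to 15.8, for a difference between two quarters. That is too imprecise against a 12-point step. An early-versus-late difference has SD 2 × 3 = 6 to 2 × 5 = 10, so it can show only large changes.

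**The case against.** **Adherence may not be inflated.** A reader might infer that adherence is bound to show a large AI influence where there is none. The documents do not support this, because adherence is undefined. Among first-reader-flagged exams the spurious gap is large; over all consensus exams it is small and can be negative. This stands, and it limits the point to an undefined measure with no comparator.

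**The SAP does not say agreement will be read as cause.** It says the objective is to explore, and it plans surveys alongside. This also stands: the risk lies in what the plan leaves open, not in a stated misuse. But self-report does not supply the missing comparison, and the objective's own question is about influence.

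**The rates are assumed.** They are, and the gap moves with them. What does not depend on them is that agreement alone cannot separate influence from shared evidence.

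**The step could mislead as a replacement.** The protocol opens any AI-generated information in the radiology system to the consensus group and does not say what is displayed, so influence may be graded. In addition, SAP 5.9 sets a missing second-reader decision equal to AI when under 1% are missing, so a set based on reader 2 would itself jump at 0.534. Both objections hold. The step should be added rather than substituted, with those exams excluded.

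**It is one exploratory objective.** This is true. The primary analysis (SAP 5.4) concerns initial-read flagging and does not use adherence.

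**Conclusion.** The concern holds in limited form. As written, the objective's question about influence cannot be answered from adherence, because agreement mixes influence with shared lesion signal and nothing planned separates them. Under zero influence and assumed values (5% flags per radiologist, 6% AI flags, 35% recall, latent correlation 0.2 to 0.5), recall differs by about 12 to 24 points by AI flag among first-reader-flagged exams and by about 2 to 7 points over all consensus exams. Sign and size depend on a measure that the SAP does not define. A reader might go further and conclude that the secondary consensus and biopsy comparisons need correcting; the documents do not support that, since neither adherence nor the proposed step enters those analyses.

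**What to change.** In SAP section 5 and 5.6.4:

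1. Define adherence by flag pattern (AI with one radiologist, AI with both, one radiologist only, both radiologists only, AI only) and label it agreement, not influence. Report recall of AI-only flags descriptively, since these exams would not reach consensus without AI.
2. Add one analysis among exams flagged by the first reader: consensus recall as a smooth function of the exam-level AI score plus a step at 0.534. Report the step with its 95% interval as the effect of the binary AI flag near the cut-off.
3. If reader 2's own decision is used for a second set, exclude exams where it was missing and set equal to AI under 5.9.
4. Examine change over time with a linear calendar trend or an early-versus-late comparison, not by quarter, and account for AI software version.
5. State that the step does not capture influence through a displayed score or other graded output, so a step near zero does not show absence of influence.

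The cost is SAP wording and one regression on data already stored. No new data collection or change to the workflow is needed.

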- Intervention Description: The AI CAD software has the product name Lunit INSIGHT MMG, which is CE certified. The version of the product that will be initially installed for this study is 1.1.6.1 (updated with future official releases). In the regular mammography screening process at the study hospital two radiologist readers review the image. During the study, AI CAD will be used as an independent third reader of screening mammograms and make a binary decision as do the other two readers (i.e., "flag" if anything suspicious is deemed present in the image, otherwise "healthy"). The AI CAD generates a continuous "score", for which a threshold value has been defined, above which the mammogram should be considered flagged, and below which it should be considered healthy. The threshold value was determined in a historic calibration dataset, in which the cut-off point resulted in a joint sensitivity of AI plus first reader radiologist which was 2% higher than the joint sensitivity of first reader and second reader radiologist. By this method the threshold value was preset to 0.534. The threshold value would not be changed during the course of the study.

Key Inclusion and Exclusion Criteria

All women attending screening mammography at Capio S:t Göran hospital will be considered for inclusion. The ethical review authority has waived the need to obtain individual written informed consent.

- Inclusion criterion: age 40-74 years, a standard four-view mammography examination was acquired (right MLO, right CC, left MLO, left CC)

- Exclusion criteria: having a breast implant (excluded by presence of either CCID or MLOID view position; ID = implant displaced) or having undergone mastectomy (excluded by not having a complete four-view mammography).

- For detailed information on planned statistical analysis – see separate Statistical Analysis Plan (SAP).

Study Type

Type of Study: Interventional study

Study design: All examinations will be reviewed by both human readers and AI CAD. During the course of the study, all mammograms that have been flagged by any of the three (human, human, AI) readers will go to a consensus discussion. The consensus discussion consists of an oral discussion of each flagged case, is held between at least two radiologists and results in a decision for each case to "recall" or to define as "healthy" (and not recall). During the course of this study, the radiologists in the

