5.5 Secondary analyses

In several of the secondary analyses we use the term **operating characteristics** referring to the various performance indicators used in evaluation of screening programs. These operating characteristics are based on the number of true and false, positive and negative, assessments by the various actors (radiologists and AI) at the various time-points (initial read, consensus discussion, tissue sampling) and based on the cancer ground truth defined by the primary end-points. Operating characteristics include sensitivity, specificity, recall rate, false negative rate, false positive rate, and the positive and negative predictive value at initial read (by each reader and by readers combined) and at consensus discussion (see Table 1). It should be noted that operating characteristics that relate to negative samples (such as the specificity, negative predictive values, and false negative rate) are not directly estimable under a screen-positive design (see Section 5.0). True and false negatives can however be estimated approximately with follow-up time, under the assumption that no new cancers develop and present clinically after the screen and that all cases are detected within the follow-up period. A longer follow-up period will increase the likelihood that cancers are discovered, but will also increase the chance of new cancers developing and being discovered. We will use a follow-up time of 23 months (the time of one screening cycle in a biennial screening program) for estimating statistics based on

estimates of true and false negatives (e.g. specificity, negative predictive values, and false negative rate). For each analysis of operating characteristics, we will perform a sensitivity analysis where women who were recalled due to symptoms (i.e., with radiologists finding no suspicious finding in the mammogram) are either excluded or re-classified as detected by all readers, AI and radiologists alike.

SENSITIVITY ANALYSES RELATED TO PRIMARY ANALYSIS

5.5.1 Repeat the primary analysis after re-classifying women who were recalled in screening due to symptoms (not due to mammographic signs) as detected by both AI and radiologists.

5.5.2 Repeat the primary analysis as a per-protocol-analysis where the examinations for which AI was not used are excluded.

5.5.3 Repeat the primary analysis without cancers with less aggressive characteristics: grade 1 in situ cancer grade 1, all in situ cancer.

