$$\text{Positive predictive value} = \frac{TP}{TP+FP}$$

$$\text{Negative predictive value} = \frac{TN}{TN+FN}$$

Table 1. Definition of operating characteristics. Ground truth is defined by pathology-verified breast cancer for the three follow-up time points described in primary end-point (4.1). It should be noted that operating characteristics that relate to negative samples (such as the specificity, negative predictive values, and false negative rate) are not directly estimable under a screen-

positive design (see Section 5.0). True and false negatives can however be estimated approximately with follow-up time, under the assumption that no new cancers develop and present clinically after the screen and that all cases are detected within the follow-up period. A longer follow-up period will increase the likelihood that cancers are discovered, but will also increase the chance of new cancers developing and being discovered. We will use a follow-up time of 23 months (the time of one screening cycle in a biennial screening program) for estimating statistics based on estimates of true and false negatives (e.g. specificity, negative predictive values, and false negative rate).

Figure 1. The actual work flow in the study. If any one of the initial readers (First Radiologist, Second Radiologist or AI) decides to flag for a suspicious finding in the image, the exam is routed to the consensus discussion. The consensus discussion consists of an oral discussion between at least two radiologists (could be same or different as the initial readers) while reviewing the images of each case, and deciding to recall the woman for further diagnostics or to determine that she is healthy.

[figure not shown]

Figure 2. Alternative scenarios for which outcomes will be analyzed. The alternative at the top of each column is the actual implementation in the study. However, based on the recorded assessments of each radiologist and AI, other alternative scenarios will be analyzed in post-study analysis. To minimize the risk of incomplete cases, for any case of initial where AI is the only reader or combined with one radiologist, and the AI process fails, the AI assessment will be replaced by a radiologist read.

[figure not shown]
[figure not shown]

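### The SAP's printed rFPF estimator, (e+f)/(f+g), contradicts its own definition, which gives (e+f)/(e+g); followed as printed, secondary false-positive results can be wrong or reversed

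*Combined protocol and SAP*

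**What the plan says.** SAP section 5 (Statistical methods) sets out a paired table. For women without the endpoint, "the endpoint=negative 2x2 table will be constructed for each stage of radiological assessments", namely reader flagging, consensus discussion and tissue sampling. The row labelled "Positive using novel reader combination including AI positive" holds e (SOC positive) and f (SOC negative). The row for a negative novel combination holds g (SOC positive) and the unknown [h] (SOC negative).

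For cancers, the SAP estimates rTPF as (a+b)/(a+c), with a standard error on the log scale of sqrt((b+c)/((a+b)(a+c))). It then says: "Analogous formulas are used for comparisons within the experimental arm and for the relative False Positive Fraction".

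For the secondary endpoints it names the "relative false positive fraction (rFPF, defined as FPF_r/FPF_{SOC} for reader combination r", and closes with the estimator: "The rFPF is estimated as $(e+f)/(f+g)$ for each stage of radiological assessments".

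**The concern.** The definition and the explicit estimator stand in the same paragraph and do not agree. Cell f holds women whom SOC did not call positive, so it cannot belong to a count of SOC false positives. Cell e holds women called positive by both strategies; it does belong there, but is left out.

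rFPF is the prespecified relative measure for three secondary endpoints. Those endpoints show what the AI combination costs women without cancer, beside a primary analysis that looks only at detection. They matter all the more at the screen-detected stage. Section 5 says that absolute specificity cannot be estimated under this design, and section 5.5 leaves statistics based on true negatives to the 23-month follow-up. An analyst who codes the printed line could report fewer false positives where there are more, or the opposite.

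**Working it through.** **Inputs.** The cell definitions, the definition of rFPF, the rTPF estimator and its interval, all from SAP section 5. The SAP states no rFPF value and no counts for e, f or g, so there is no figure to reproduce. Every count below is an assumption chosen for illustration.

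**From the definition.** Let N = e+f+g+h be the women without the endpoint.

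- FPF of the novel combination = (e+f)/N
- FPF of SOC = (e+g)/N
- Ratio = (e+f)/(e+g); the unknown h cancels

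**From the analogy.** Replacing a, b, c by e, f, g in (a+b)/(a+c) also gives (e+f)/(e+g). The inverse orientation that the SAP allows for rTPF would give (e+g)/(e+f). Neither is (e+f)/(f+g). The sum f+g corresponds to b+c, which belongs under the square root of the interval.

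**Size of the discrepancy.** Printed value = defined value × (e+g)/(f+g). The two agree only if e = f. The printed value is too high when e > f and too low when e < f.

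**Direction.** The defined ratio exceeds 1 when f > g. The printed ratio exceeds 1 when e > g, which is not the comparison of interest. The two fall on opposite sides of 1 when f < g < e or e < g < f.

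**Interval by analogy.** exp(log rFPF ± 1.96 × sqrt((f+g)/((e+f)(e+g)))). For case A below, sqrt(600/(1000 × 1200)) = 0.0224, giving 0.798 to 0.871.

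| Case | e | f | g | Defined (e+f)/(e+g), 95% CI | Printed (e+f)/(f+g) |
|---|---|---|---|---|---|
| A | 800 | 200 | 400 | 1000/1200 = 0.83 (0.80 to 0.87) | 1000/600 = 1.67 |
| B | 1500 | 300 | 600 | 1800/2100 = 0.86 (0.83 to 0.88) | 1800/900 = 2.00 |
| C | 1000 | 2000 | 1500 | 3000/2500 = 1.20 (1.15 to 1.25) | 3000/3500 = 0.86 |
| D | 1000 | 500 | 500 | 1500/1500 = 1.00 (0.96 to 1.04) | 1500/1000 = 1.50 |

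**Equal false positives.** If f = g, the defined ratio is 1. Writing p = e/(e+f) for the share of the novel combination's false positives that SOC also makes, the printed ratio is 1/(2(1−p)): 0.63 at p = 20%, 1.00 at 50% and 2.50 at 80%.

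**Triple read against SOC, at flagging.** In the protocol's study design, mammograms "flagged by any of the three (human, human, AI) readers will go to a consensus discussion". The Figure 2 legend confirms that this workflow is among the scenarios analysed: "The alternative at the top of each column is the actual implementation in the study". Whatever SOC flags is then also flagged by the triple read, so g = 0. The defined ratio becomes 1 + f/e and the printed one 1 + e/f. With e = 1000, raising the AI-only false positives f from 250 to 500 moves the defined ratio from 1250/1000 = 1.25 to 1500/1000 = 1.50. The printed ratio falls from 1250/250 = 5.00 to 1500/500 = 3.00, so more false positives look like an improvement.

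**The case against.** The strongest reply is that this is a one-letter slip that a careful programmer would catch. The definition and the sentence on analogous formulas both lead to (e+f)/(e+g), and only the printed expression disagrees. The Preface places the secondary endpoints in later publications, which leaves time to correct it. Other false-positive measures are planned independently: section 5.5 says "Operating characteristics include sensitivity, specificity, recall rate, false negative rate, false positive rate" and more, and Table 1 gives separate formulas for the false positive rate and recall rate. All of that is fair, and it limits the harm. It does not make the printed estimator right: the one explicit formula for this measure is the wrong one, and the SAP should not leave the choice to whoever writes the code.

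Two further points stand as qualifications. First, the text was read from PDF by a program and the issue turns on one letter, so the source file should be checked; the expression is well formed and shows no sign of a misread. Second, not every illustration suits every comparison. When AI plus the first reader is set against both readers, the first reader is in both strategies, so all of that reader's false positives fall in e and g holds only second-reader false positives. Case C, and the 20% overlap figure, would then need a second reader with far more false positives than the first. They fit better a comparison such as AI alone against SOC. Cases A and B and the triple-read example do not have this difficulty.

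**Conclusion.** The concern holds. By the SAP's own table and definition the estimator is (e+f)/(e+g), and the printed (e+f)/(f+g) is correct only in the special case e = f. This follows from algebra and rests on no outside source. How far the results would be off cannot be known from the documents, since e, f and g are not given. Under the assumed counts the printed value ranges from modestly wrong to reversed, with reversal whenever g lies strictly between e and f.

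The effect is confined to the secondary rFPF results at flagging, consensus and tissue sampling. The primary rTPF estimator, its confidence interval, the 0.85 margin and the sample size do not use this formula. It should be fixed before the secondary analyses are programmed.

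**What to change.** In SAP section 5, replace the estimator with rFPF = (e+f)/(e+g), and print its interval in full: exp(log rFPF ± 1.96 × sqrt((f+g)/((e+f)(e+g)))). Check the source file first, to confirm that the printed letter is f.

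One typographical correction can be made at the same time. The rule for switching from non-inferiority to superiority gives the interval level as 2(1−α)×100%, which is 195% at α = 0.025. It should read (1−2α)×100%, which is the two-sided 95% that the SAP states elsewhere in that section.

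The cost is one corrected formula and one corrected expression in a SAP revision. Data collection, sample size and participants are not affected.
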